## Study Description

The research will involve 50 female patients who have undergone liposuction and will be divided into two groups.

**Group Intraoperative fluid ratio:** Fluid administration will be determined by the intraoperative fluid ratio. This ratio is calculated by dividing the sum of subcutaneous infiltration and intravenous fluid by the total aspirate volume. Depending on the aspiration volume, it will be maintained at 1-1.4.

**Group Carotid Artery Peak Velocity Variation:** Participants will be given a fluid maintenance rate of 1.5 ml/kg/h. To determine fluid responsiveness, the carotid artery peak velocity variation ( $\Delta V_{Peak-CA}$ ) will be measured before, during, and after the procedure. If the  $\Delta V_{Peak-CA}$  goes above 15%, the patient will receive a fluid bolus of lactated ringer solution at a rate of 4-6 ml/kg over 10-15 minutes, and the team will re-measure fluid responsiveness 10 minutes after each  $\Delta V_{Peak-CA}$ .

During the examination, a single cardiothoracic anesthesiologist will use a 13-6 MHz linear probe (Fujifilm Sonosite M-Turbo) to measure the peak velocity of the carotid artery on the left side. The sample volume will be positioned at the center of the lumen, 2 cm from the bulb, and a pulsed wave Doppler examination will be conducted.

To measure the  $\Delta V_{Peak-CA}$ , the investigators will calculate the maximum and minimum values during one respiratory cycle. This will be done by using the formula:  $100 \times (\text{maximum peak velocity} - \text{minimum peak velocity}) / [(\text{maximum peak velocity} + \text{minimum peak velocity})/2]$ .

## Surgical technique

The superwet tumescence technique will be the only method utilized for infiltration during the procedure. All participants will undergo power-assisted liposuction, and a single surgeon will operate. The wetting solution will contain 1000cc of normal saline and 2mg of epinephrine in a 1:500,000 ratio. The total infiltration volume will depend on the participant's surgery characteristics. The total amount of aspiration will depend on the participant and surgery plan and can vary between 2500 to 5000 ml

During the surgical procedure, the investigators will monitor vital signs such as blood pressure, heart rate, temperature, oxygen levels, and urine output. Additionally, the investigators will track the amount of fluids given and removed and the volume of blood aspirated.

Following surgery, participants will be hospitalized for 24 hours. During this time, the investigators will closely monitor the plethysmography variability index (PVi) in both groups.

If the PVi exceeds 15%, patients will receive a ringer lactate fluid bolus of 4-6 ml/kg over 10-15 minutes. Additionally, the investigators will keep track of their urine output, total fluid balance, and vital signs

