## **Arms and interventions**

Experimental: Group Carotid Artery Peak Velocity Variation

Participants will be given a fluid maintenance rate of 1.5 ml/kg/h. To determine fluid responsiveness, the carotid artery peak velocity variation ( $\Delta V_{Peak-CA}$ ) will be measured before, during, and after the procedure. If the  $\Delta V_{Peak-CA}$  goes above 15%, the participant will receive a fluid bolus of lactated ringer solution at a rate of 4-6 ml/kg over 10-15 minutes, and the team will re-measure fluid responsiveness 10 minutes after each  $\Delta V_{Peak-CA}$ .

Active Comparator: Group Intraoperative fluid ratio

The intraoperative fluid ratio will determine fluid administration. This ratio is calculated by dividing the sum of subcutaneous infiltration and intravenous fluid by the total aspirate volume. Depending on the aspiration volume, it will be maintained at 1-1.4.

This ratio is calculated by dividing the sum of procedure subcutaneous infiltration and intravenous fluid by the total aspirate volume during surgery

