## **Outcome Measures**

Primary Outcome

1.- Mean Postoperative PVi

Following surgery, participants will be hospitalized for 24 hours. Throughout this period, we will keep a close eye on the Plethysmography Variability Index in both groups. The PVi is a dynamic index that measures the relative variability of the plethysmography waveform detected noninvasively from a pulse oximetry sensor, ranging from 0 to 100. By automatically calculating the dynamic changes that occur during the respiratory cycle, it uses the detected amplitudes. A higher variability in the plethysmography waveform has been linked to preload dependence and fluid responders. If the PVi exceeds 15%, the patient will receive a fluid bolus of lactated ringer solution at a rate of 4-6 ml/kg over 10-15 minutes.

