## 2.- Postoperative intravenous fluid balance

Following surgery, participants will be hospitalized for 24 hours. During the postoperative period, the investigators will keep track and document the exact volume of fluid administered in milliliters.

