### 6.- The intraoperative intravenous fluid balance

Throughout the surgical procedure, the investigators will meticulously monitor and record the precise amount of fluid administered in milliliters.

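### A primary outcome, postoperative IV fluid in ml, depends partly on a bolus that staff may size from 4 to 6 ml/kg and, in the experimental arm only, on a second bolus trigger

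*Combined protocol and SAP*

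**What the plan says.** Postoperative intravenous fluid balance is item 2 in Outcome Measures. It comes before the secondary heading, so it is a primary outcome. It is defined by volume, not by volume per kg: "During the postoperative period, the investigators will keep track and document the exact volume of fluid administered in milliliters". Its intraoperative counterpart, secondary item 6, reads: "Throughout the surgical procedure, the investigators will meticulously monitor and record the precise amount of fluid administered in milliliters".

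Two rules can add a bolus.

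- **Both arms, after surgery.** Under Surgical technique, "the investigators will closely monitor the plethysmography variability index (PVi) in both groups" for 24 hours, and "If the PVi exceeds 15%, patients will receive a ringer lactate fluid bolus of 4-6 ml/kg over 10-15 minutes". Nothing says how to choose within 4-6 ml/kg.
- **Experimental arm only.** Under Arms and interventions, carotid peak velocity variation "will be measured before, during, and after the procedure". When it rises above 15%, "the participant will receive a fluid bolus of lactated ringer solution at a rate of 4-6 ml/kg over 10-15 minutes".

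The plan does not say when surgery ends and the postoperative period begins, or when carotid-guided dosing stops. The text available describes no masking, but part of the document was not available for review, so only the absence of a description can be stated. Statistical analysis specifies Student's t-test or a Chi-square test at 0.05.

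**The concern.** The trial compares two intraoperative fluid strategies partly by how much fluid patients need afterwards. That comparison is clean only if the rule turning need into ml is the same in both arms. It may not be, for two reasons.

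- **Dose choice.** Staff choose within a range whose top is 50% above its bottom. If that choice drifted with knowledge of the arm, equal need would produce unequal ml.
- **A second trigger in one arm.** A carotid bolus given after surgery adds directly to the outcome in the experimental arm. It may also prevent later PVi boluses there, since "A higher variability in the plethysmography waveform has been linked to preload dependence and fluid responders". This route needs no drift in dosing.

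A significant t-test on ml could then partly reflect bolus sizing or the extra trigger, and not how well each strategy had filled the patient by the end of surgery. Mean postoperative PVi, the other primary outcome, is only a partial check because boluses also change it.

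**Working it through.** The plan gives no effect size, SD or power, so there is no figure of its own to reproduce.

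**Inputs from the documents.** 50 patients in two groups (Study Description); bolus 4-6 ml/kg; t-test at 0.05.

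**Assumptions.** 25 per arm, two-sided test, weight 70 (SD 10) kg, equal need in both arms, a mean of 1, 2 or 3 PVi triggers per patient.

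**Size of one bolus.** 4 × 70 = 280 ml; 6 × 70 = 420 ml; spread 140 ml.

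**Two models, 20,000 simulated trials per scenario.**

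- Dose-independent: trigger counts are Poisson and ignore fluid already given.
- Deficit: each patient has a gamma deficit (shape 2, mean 5, 10 or 15 ml/kg) and receives boluses until within 2 ml/kg of full correction.

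**Dose choice: share of trials significant under equal need**

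| PVi dose by arm | Dose-independent, 1/2/3 triggers | Deficit, mean 5/10/15 ml/kg |
|---|---|---|
| Fixed 5 ml/kg, or random 4-6 with no lean | 5% | 5% |
| 4.75 vs 5.25 ml/kg | 6/7/9% | 6/5/5% |
| 4.5 vs 5.5 ml/kg | 10/15/21% | 8/6/5% |

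If 36 ml/kg of maintenance fluid (1.5 ml/kg/h × 24 h, assumed for both arms) is in the total, the last row becomes 7/10/15% and 6/5/5%. The extreme of 4 vs 6 ml/kg in every bolus gives about 25/46/62% in the dose-independent model.

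*Hand check, 4.5 vs 5.5, dose-independent, mean k triggers.* The false gap is 1 × 70 × k ml. The per-patient variance is about 5² × (5000k + 100k²), where 5000 = 70² + 10². For k = 2 this is 25 × 10,400 = 260,000, so the SD is 510 ml. The standard error of the difference is 510 × √(2/25) = 144 ml. The gap is 140 ml, and 140/144 = 0.97 standard errors. Against the critical value 2.01 (48 df), the chance of significance is about 15%, as simulated.

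**Carotid bolus: 5 ml/kg, PVi dose fixed at 5 ml/kg, counted as postoperative**

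| Share of experimental arm receiving it (assumed) | Mean added ml (5 × 70 × share) | Dose-independent, 1/2/3 triggers | Deficit |
|---|---|---|---|
| 10% | 35 | 6/6/6% | not run |
| 20% | 70 | 10/8/7% | 5% |
| 30% | 105 | 16/11/9% | 5% |
| 50% | 175 | 36/22/16% | 5% |

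The deficit figures stay near 5% because the carotid bolus then replaces a later PVi bolus. The exception is the cell with mean deficit 5 ml/kg and half the arm treated: it reaches 7% if patients with little deficit also receive the bolus.

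**The same bolus counted as intraoperative.** Dose-independent: 5% throughout. Deficit: 11/7/6%, 19/10/7% and 43/21/12% for 20%, 30% and 50% receiving it.

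**ml against ml/kg.** Power for a true 1 vs 2 triggers at 5 ml/kg is 0.81 in ml and 0.82 in ml/kg. With the assumed maintenance in the total it is 0.51 and 0.82. Working in ml/kg does not remove a lean: 4.5 vs 5.5 still gives 10/16/22% in the dose-independent model.

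**The case against.** The case against has four parts.

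- **The PVi rule is the same in both arms.** Trigger, range and infusion time match, and nothing in the plan suggests that dosing will lean by arm. A narrow weight-based range is ordinary clinical latitude. This stands: a reader might infer that the range itself biases the outcome, but without a lean the error rate is 5%. Nor can it be said that the trial is unmasked, only that no masking is described in the text available.
- **The carotid bolus does have a place.** A reader might infer that it belongs to no fluid outcome. Item 2 counts all fluid in the postoperative period whatever the trigger, so a bolus after surgery falls there. What is missing is the boundary between the two periods.
- **Extra fluid in one arm is a real difference.** If the experimental strategy gives more fluid after surgery, item 2 measures exactly that, so significance from this source is not purely type I error. This also stands. What remains is interpretation: the difference comes from a second trigger, not from greater need under a common rule.
- **Counting the bolus as intraoperative is no repair.** It might look like the natural correction, but it goes against the plain wording of items 2 and 6. In the deficit model, the one closer to the plan's account of PVi, it raises significance from about 5% to 6-43%.

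The objection does not remove the undefined boundary, the open dose, or the fact that only one arm has a second trigger that can feed a primary outcome.

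**Conclusion.** The point holds, is conditional, and is minor. A primary outcome in ml has one discretionary input (the PVi bolus size) and one arm-specific input (the after-procedure carotid bolus), and the plan does not define when the postoperative period starts.

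The discretionary input does no harm without a lean. With 4.5 vs 5.5 ml/kg the false-positive rate is about 5-21%, depending on trigger count and model. The arm-specific input, counted as postoperative, gives about 5-36%, depending on how often it is given and whether it replaces later PVi boluses; part of that is a true difference in fluid given. Body weight, trigger counts, lean and carotid-bolus frequency are all assumed, so these ranges show what could happen and do not estimate what will.

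**What to change.** 1. Set one postoperative PVi bolus dose inside the existing range, for example 5 ml/kg, for both arms, and record the reason for any clinical deviation.
2. Define the end of surgery. Finish carotid measurement and carotid-guided dosing by then, before handover, so that only the common PVi rule triggers boluses in the postoperative period. Report fluid by trigger. If a carotid bolus is nevertheless given after surgery, show item 2 with and without it, and do not present moving it to item 6 as a correction for bias.
3. Analyse postoperative volume in ml/kg, since the bolus is dosed per kg. The gain is small unless maintenance fluid is in the total.

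The cost is a few wording changes and one or two extra lines in the report, with no added patients, staff or equipment. The downside is slightly less clinical freedom over dose. The changes work together: a single dose closes the first route but not the second, and ml/kg closes neither.

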## **Arms and interventions**

Experimental: Group Carotid Artery Peak Velocity Variation

Participants will be given a fluid maintenance rate of 1.5 ml/kg/h. To determine fluid responsiveness, the carotid artery peak velocity variation ( $\Delta V_{Peak-CA}$ ) will be measured before, during, and after the procedure. If the  $\Delta V_{Peak-CA}$  goes above 15%, the participant will receive a fluid bolus of lactated ringer solution at a rate of 4-6 ml/kg over 10-15 minutes, and the team will re-measure fluid responsiveness 10 minutes after each  $\Delta V_{Peak-CA}$ .

Active Comparator: Group Intraoperative fluid ratio

The intraoperative fluid ratio will determine fluid administration. This ratio is calculated by dividing the sum of subcutaneous infiltration and intravenous fluid by the total aspirate volume. Depending on the aspiration volume, it will be maintained at 1-1.4.

This ratio is calculated by dividing the sum of procedure subcutaneous infiltration and intravenous fluid by the total aspirate volume during surgery

## **Outcome Measures**

Primary Outcome

1.- Mean Postoperative PVi

Following surgery, participants will be hospitalized for 24 hours. Throughout this period, we will keep a close eye on the Plethysmography Variability Index in both groups. The PVi is a dynamic index that measures the relative variability of the plethysmography waveform detected noninvasively from a pulse oximetry sensor, ranging from 0 to 100. By automatically calculating the dynamic changes that occur during the respiratory cycle, it uses the detected amplitudes. A higher variability in the plethysmography waveform has been linked to preload dependence and fluid responders. If the PVi exceeds 15%, the patient will receive a fluid bolus of lactated ringer solution at a rate of 4-6 ml/kg over 10-15 minutes.

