### 5.- Mean arterial blood pressure during hospitalization

Following surgery, participants will be hospitalized for 24 hours. During this time, the investigators will monitor mean arterial pressure.

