## Statistical analysis

We will express continuous variables as means with standard deviation and percentages for categorical variables. To test the data statistically, we will use Student's t-test or Chi-square test depending on the appropriateness. P-values less than 0.05 will be considered statistically significant. The analyses and calculations will be performed using SPSS Statistics 21.0 (IBM, NY, USA).

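### Mean postoperative PVi and postoperative mean arterial pressure are compared without a baseline covariate, which gives up precision that a short pre-induction reading could recover

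*Combined protocol and SAP*

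**What the plan says.** - **Outcome Measures, primary outcome 1.** The outcome is "Mean Postoperative PVi", taken over the 24 hours in hospital after surgery. PVi is described as a noninvasive index from a pulse-oximetry sensor. Here and under Surgical technique, PVi monitoring is described only for the postoperative period, in both groups.
- **Secondary outcome 5.** Over the same 24 hours, "the investigators will monitor mean arterial pressure". No pre-intervention value enters the definition.
- **Surgical technique.** During the operation, "the investigators will monitor vital signs such as blood pressure, heart rate, temperature, oxygen levels, and urine output". Blood pressure is therefore measured intraoperatively, but no reading is fixed before fluids begin.
- **Study Description.** "The research will involve 50 female patients who have undergone liposuction and will be divided into two groups". No allocation ratio, allocation method, target difference or power is given.
- **Statistical analysis.** For all outcomes, "we will use Student's t-test or Chi-square test depending on the appropriateness", and "P-values less than 0.05 will be considered statistically significant". No covariate, baseline adjustment or regression model is named.

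The only measurement stated to be taken before the procedure is the carotid velocity variation, and it is described for the experimental arm only.

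**The concern.** With 50 patients, a two-sample t-test has good power only for large differences. Part of the spread in a postoperative mean may reflect stable differences between patients that were already present before surgery. A baseline value used as a covariate removes that part from the error term. Without one, it stays in the standard error, and a chance difference in starting values between the arms can be neither seen nor allowed for.

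At stake is the precision of one of the two primary comparisons and of one secondary comparison. Recovering some of it would need no further recruitment. The sensor is already used for every patient after surgery, and blood pressure is already monitored during it.

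**Working it through.** The plan gives no power, SD or target difference, so there is no stated figure to reproduce. Results are in units of the outcome's SD.

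**Inputs**
- N = 50 in two groups (Study Description). An equal split, 25 per arm, is assumed.
- Level 0.05 (Statistical analysis). Two-sided testing is assumed.
- The correlation r between baseline and outcome is not in the documents. A range from 0 to 0.6 is assumed.

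**Step 1: unadjusted t-test**
- Standard error of the difference = √(1/25 + 1/25) = √0.08 = 0.283 SD, with 48 degrees of freedom.
- Power comes from the noncentral t distribution with noncentrality d/0.283. Setting power to 80% gives d = 0.81 SD.
- At d = 0.7 SD the noncentrality is 0.7/0.283 = 2.47 and power is 68%.
- A 20/30 split would raise the detectable difference only to 0.83 SD, so the equal-split assumption matters little.

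**Step 2: ANCOVA with arm and one baseline value**
- Variance relative to the t-test = (1 − r²) × (1 + 1/46). The second factor is the expected cost of chance imbalance in the covariate, 1 + 1/(N − 4). Error degrees of freedom are 47.
- Equivalent unadjusted sample size = 50 divided by that factor.

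| r | 1 − r² | Net variance factor | Equivalent N | Detectable at 80% power | Power at 0.7 SD |
|---|---|---|---|---|---|
| t-test | – | 1.00 | 50 | 0.81 SD | 68% |
| 0 | 1.00 | 1.02 | 49 | 0.82 SD | 67% |
| 0.2 | 0.96 | 0.98 | 51 | 0.80 SD | 69% |
| 0.3 | 0.91 | 0.93 | 54 | 0.78 SD | 71% |
| 0.5 | 0.75 | 0.77 | 65 | 0.71 SD | 79% |
| 0.6 | 0.64 | 0.65 | 76 | 0.65 SD | 85% |

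A simulation of 6,000 trials each at r = 0.3 and r = 0.5, with a true difference of 0.81 SD, gave ANCOVA power of 82.7% and 89.0%. The formula gives 82.7% and 89.2%.

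**Step 3: chance baseline imbalance**
- The between-arm difference in baseline means has SD √(2/25) = 0.28 SD.
- It enters the unadjusted estimate multiplied by r: 0.3 × 0.283 = 0.08, 0.5 × 0.283 = 0.14 and 0.6 × 0.283 = 0.17 SD.

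**The case against.** An unadjusted t-test on a postoperative mean is a legitimate choice. The strongest argument against changing it is that the benefit rests on a correlation the documents do not give, and which the design may make low for PVi. A few minutes before induction would have to predict a 24-hour mean that follows infiltration, 2500 to 5000 ml of aspiration and arm-specific fluid. A PVi above 15% also triggers a bolus in both arms, so treatment acts on the outcome itself and may weaken its link to baseline. This stands as a caveat. It argues for modest expectations, but the trade remains favourable: about one point of power at r = 0 against about 11 points at r = 0.5 for a true difference of 0.7 SD (79% against 68%). No comparable MAP-triggered bolus is described for outcome 5.

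A second argument is that feasibility is inferred. This also stands in part. No section places PVi monitoring before or during surgery, and no time is given for a reading. Blood pressure is monitored during the operation, but the documents do not say that a reading precedes the allocated fluid. A usable MAP baseline therefore cannot be assumed to exist already; it has to be specified.

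A reader might also infer three stronger points that the documents do not support:
- **That the primary comparison is biased.** Under random allocation, chance imbalance is already reflected in the t-test's standard error, and omitting baseline costs precision only. The allocation method is not described, so this review does not claim bias on that ground.
- **That the full 0.28 SD imbalance passes into the estimate.** Only r times that amount does.
- **That every continuous outcome is a postoperative value lacking a baseline.** Intraoperative urine volume (outcome 3) and intraoperative fluid (outcome 6) are measured during surgery. The point concerns outcomes 1 and 5 only.

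**Conclusion.** The point holds as a missed gain in precision for outcomes 1 and 5. With 25 per arm and two-sided 0.05, both assumed, baseline ANCOVA would lower the detectable difference from 0.81 SD to between 0.78 and 0.65 SD for r from 0.3 to 0.6. That is the precision of about 54 to 76 unadjusted patients. The gain is modest at r = 0.3, material from about 0.5 and negligible at 0.2 or below. Which of these applies cannot be settled from the documents, and MAP is more likely than PVi to reach the upper part of the range. The change is worth making because it is cheap and its downside is small. The planned test is not invalid.

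**What to change.** 1. In both arms, record MAP and a short noninvasive PVi reading before induction and before any arm-specific fluid starts. A value taken once the allocated fluid strategy is under way would not be a valid baseline.
2. Prespecify in the Statistical analysis section that outcomes 1 and 5 are analysed by ANCOVA, with arm and the matching baseline value as terms.
3. Keep the unadjusted t-test as a sensitivity analysis for both outcomes.

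**Cost:** a short extra PVi reading, one or two data fields, a sentence in the analysis section and one degree of freedom. If r proves low, little is gained. No treatment rule changes.
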